## **2.5.8 Security Assessment and Control**

The health risks of the research subjects are not related to the interventions and procedures envisaged in the study. The clinical-diagnostic and treatment approaches used in the research process are routinely used in real-life medical care for patients with the clinical characteristics of interest in the study. Diagnostic tools and treatments are standardized.

The genotyping of CYP2C19 \*2, \*3 alleles performed on randomly selected patients in the experimental group belongs to the category of laboratory-diagnostic procedures and does not pose a health risk.

The antiplatelet drugs such as clopidogrel or alternative P2Y12 inhibitors selected for treatment in this laboratory study are commonly prescribed drugs in everyday, real-world clinical practice. Their use is recommended by current guidelines in the setting of routine PCI. Patient-tailored treatment selection of these drugs based on the results of CYP2C19 \*2, \*3 genotyping increases the chances of preventing MACCE and, therefore, cannot be considered as an additional health hazard for the study subjects.

Health risks are not related to the initial assessment and ongoing follow-up of study subjects, which are conducted to determine inclusion and exclusion criteria, and to monitor clinical outcomes of the study.

Health risks to study subjects are primarily related to the development of the disease under study, such as CAD, MACCEs (cardiovascular death, nonfatal myocardial infarction, recurrent angina, repeated PCI, stent thrombosis, ischemic stroke, transient ischemic attack, intracerebral hemorrhagic stroke), and known, expected, adverse effects of drug treatment (intracerebral hemorrhage, GI bleeding, other bleeding, thrombotic thrombocytopenic purpura).

In some cases, health risks may also be due to the results of medical care measures taken outside the scope of the study, including inappropriate or erroneous.

During the observation period, patients will undergo the following clinical-diagnostic examinations, the results of which will assess health risks related to the study disease and treatment:

At each follow-up visit or withdrawal, patients will undergo a medical examination and clinical tests:

- to assess the disease/condition of interest;
- to identify the risk of known, expected, adverse events of MACCE and drug treatment;
- to assess possible comorbidities/conditions;
- to control lifestyle-related risks;
- to review the results of diagnostic tests and treatment interventions performed outside the study;

These diagnostic measures of clinical case observation are routinely used in real-life clinical practice.

To assess the risks posed by the results of potentially inappropriate or erroneous medical care performed outside the scope of the study, the results of clinical and laboratory tests available at that time will be used. The possible effects of medical care provided to the patient outside the study on the health status and study processes will be assessed within the framework of the study's planned monitoring measures. Such effects may include:

- medical care;
- place of care;
- medication;
- diagnostic or treatment procedure;
- diagnosis.

Health risks for study subjects may be associated with non-adherence to medication treatment. Using the BMQ, potential barriers and risks to the use of prescribed treatment will be assessed at all points of observation included in the study. This will make it possible to avoid risks associated with sporadic cases of non-adherence.

The results of monitoring and evaluation during the study will reveal possible deviations from the study procedures, which may be associated with other unforeseen health hazards and will make it possible to avoid them.

In order to avoid threats to the right to choose, freedom of choice and confidentiality of research subjects, the following research-related procedures should be implemented in all cases:

- Providing complete written and narrative information about research operations
  - Detailed explanations of the study protocol;
  - Objectives, measures and procedures;
  - Expected risks, benefits and consequences;
  - Collection, storage and processing of patient identification and clinical data in accordance with the objectives of the research;
  - Measures for the protection of personal data and conditions for transfer;

- Obtaining informed consent from the patient to participate in the research based on an independent decision following the principles of the Declaration of Helsinki;
- Implementing data collection and processing procedures following the conditions set out in the 2018 EU General Data Protection Regulation (GDPR)
  - Identification of the persons conducting the research, legal processing and controlling of the data and authorization for access to the processing of the study data;
  - Coding of the study participants' personal identification data within the framework of the research with its other unique identifier, which will be stored confidentially, on paper and in an electronic file during the research period, in a physical space, on a personal computer or domain and will be accessible only to personnel authorized in the study;
  - Storage and protection of primary medical documents (clinical, laboratory or imaging examination results, reports, images, instrumental records or other, produced in digital or paper form) in the medical card following the current rules, conditions, forms and practices;
  - Entering the data of study interest into a data record form (CRF) without personal data identifying the study participants, with a subject-specific, coded, unique identifier (e.g., number) and protecting it in a physical space that will be accessible only to authorized study personnel;
  - Entering the data of study interest into an electronic database by encoding the names of the data (including variables) and without study participants personal data identifiers with subject-specific, coded, unique study identifiers and protecting it in an electronic file or domain, in such a way that it is accessible only to authorized study personnel;
  - Processing and transmitting the study data without the study participants' personal identifiers in an encrypted (coded) form and through a protected communication channel only to authorized study personnel;
  - Transfer of own data to the research subject in aggregate form, in the form of a report and based on a formal request;
  - Storage of the results of legal data processing, de-identified data for an indefinite period and for the purposes of the study;
  - Destruction of the blood sample taken for the CYP2C19 genotype testing in accordance with the established procedure upon completion of the laboratory analysis provided for in the study;
  - Deletion of the study participants' personal identification data on paper and from electronic databases and data collection forms within 1 year after the study completion;

The results of monitoring and evaluation carried out throughout the study period will reveal the risks of possible deviations from operational procedures, which may be associated with unforeseen threats of data breaches and illegal processing, and will make it possible to avoid them.

## **2.5.9 Processing of Biological Study Material**

As part of the study, blood samples from study participants will be processed for CYP2C19 genotyping. In addition, during the observation period, study subjects may undergo routine clinical tests by processing blood and urine samples.

Laboratory testing for CYP2C19 genotyping should be performed on at least 160 patients randomized to the study treatment arm for clopidogrel or an alternative P2Y12 inhibitor treatment intervention and for allocation to the appropriate study arm. Blood samples will be processed for this analysis only once during the study period.

The sample laboratory examination for CYP2C19 \*2, \*3 allele genotyping will be carried out in the Ltd "Vistamedi" diagnostic laboratory.

The analysis requires a 3 ml venous blood sample, obtained by simple venipuncture manipulation. The blood sample will be collected at the research center. The blood sample is immediately placed in a K3 EDTA type tube.

The tube label must be marked with the patient's unique number in the study. Along with the blood sample preparation, a sample form (paper) must be filled out, accompanying the sample during transportation to the laboratory. The sample form must include:

- The patient's unique number or code in the current study;
- The sample tube number (or the tube barcode must be marked).
- Sample volume;
- Purpose of the sample, name of the test.
- Place of sample collection;
- Time of sample collection;
- Time of sample shipment;
- Method of transportation;

The sample should be transported to the laboratory in a special blood sample transport container that ensures compliance with the transportation temperature (from -20° to -80°) regime.

Upon receipt in the laboratory, the sample with the accompanying form will be stored in a storage space (refrigerator) with a temperature regime from -20° to -80°, accessible to authorized study personnel.

The obtained sample will be subjected to analysis for CYP2C19 \*2, \*3 allele genotyping using the RT-PCR-based allele discrimination method. The analytical procedures include the stages of DNA extraction from the obtained blood sample, pre-PCR and PCR, which are performed using DNA extraction reagents and appropriate primers. Appendix 2 presents the main procedural descriptions of the analytical phase of CYP2C19 \*2, \*3 allele genotyping that should be applied in the study.

The procedures of the post-analytical stage of the laboratory study include the analysis of the measurement results obtained at the RT-PCR stage, the formation of the final test result, and the documentation of the study result in the form of a report.

The laboratory study report will be transmitted to the researcher, authenticated in the study and the patient. The study investigator will enter the result reflected in the report into the clinical case registration form.

After that, the remains of the biological material sample will be destroyed according to the procedures adopted in the laboratory.

During the initial assessment and follow-up period, blood and urine samples of the study participants involved can be collected and processed by the medical care team and the study center investigator for various laboratory-diagnostic tests as part of the ongoing clinical assessments - at the end of the 3rd, 6th and 12th months and in case of early withdrawal of the participant from the study or at any time during the follow-up. These laboratory tests may be performed as routine diagnostic tests in real-world practice in an accredited diagnostic laboratory of the study center or other medical institution using conventional (generally accepted) methods for performing these tests.

The results of the tests performed in the laboratory of the study center or other medical institution within the follow-up period can be collected in the patient's outpatient medical record as a routine practice. The investigator may transfer the results of these diagnostic tests to the study case registration form and then use them for the purposes of the study.

The patient's outpatient medical record will also include the results of other laboratory tests used for routine management of the patient's condition, which are not of interest to the study, although they can be used to characterize the study's endpoints.

## **2.5.10 Schedule of Study Visits**

A schematic description of the screening, randomization, and follow-up procedures is provided in Appendix 4 in tabular form.

## **2.6 Evaluation of Study Results**

### **2.6.1 Study Endpoints**

The study follow-up results will be discussed and presented by study arms, as well as concerning the primary and secondary endpoints of the study.

The study results will also be discussed concerning other endpoints, which will be represented by clinical or non-clinical data and characterize the factors that affect the efficacy of antiplatelet treatment and determine the clinical and non-clinical outcome in the course of the CCSs both with and without the results of CYP2C19 genotyping.

The indicators for assessing the effectiveness of the study are presented in Appendix 5.

In the study, the selection of treatment regimens with clopidogrel and an alternative P2Y12 inhibitor will be carried out by determining the genotype of the CYP2C19 \*2, \*3 non-functional alleles. Clopidogrel will be used in study participants with CYP2C19 \*2, \*3 normal allele genotypes and in the control arm of study participants not undergone CYP2C19 genotyping – unspecified CYP2C19 genotype. Study participants with CYP2C19 \*2, \*3 non-functional allele genotypes will be given alternative antiplatelet therapy.

In cases of CAD, regardless of treatment with P2Y12 inhibitors after ePCI, the clinical endpoints will be represented with MACCEs and other clinical conditions related to CAD or the potential adverse events of antiplatelet drug treatment. The incidence of the primary, secondary and other study endpoints defined as clinical outcomes of CYP2C19 genotype-guided P2Y12 inhibitor treatment will be assessed in the study arms.

The primary endpoints of the study are defined as:

- Number of study participants who died from any cause (Death from Any Cause) within a 12-month of the study follow-up;
- Number of study participants who died from any cardiovascular cause (Death from Cardiovascular Cause) within a 12-month of the study follow-up;

The secondary endpoints of the study are defined as:

- Number of study participants who experienced non-fatal myocardial infarction (Non-fatal Myocardial Infarction) within a 12-month of the study follow-up;
- Number of study participants who experienced unstable angina or angina requiring hospitalization (Unstable Angina) within a 12-month of the study follow-up;
- Number of study participants who experienced a stroke or transitory cerebral ischemic event (Stroke or TIA) within a 12-month of the study follow-up;
- Number of study participants who experienced major bleeding (Major Bleeding) within a 12-month of the study follow-up;

- Number of study participants who experienced non-major bleeding (Non-major Bleeding) within a 12-month of the study follow-up;
- Number of study participants who experienced a heart failure event (Heart Failure Event) within a 12-month of the study follow-up;
- Number of study participants who experienced percutaneous coronary intervention or coronary artery bypass-grafting (Repeated Coronary Revascularization) within a 12-month of the study follow-up;

Pre-specified endpoints of the study are defined as:

- Number of study cases in each arm with a composite of death from any cause, myocardial infarction, stroke, or major bleeding (Net adverse clinical events - NACEs) within a 12-month of the study follow-up;
- Number of study cases in each study arm with a composite of death from any cause, myocardial infarction, or stroke (Major adverse cardiac or cerebral events - MACCEs) within a 12-month of the study follow-up;
- Number of study participants who reported their health status as good or satisfactory, or with the appearance of CVD symptoms, or with a significant inability to self-care (Patient-Reported Health Status) at 3, 6 and 12 months of the study follow-up;
- Number of study participants self-reported angina not required hospitalization (Patient-Reported Angina Not Required Hospitalization) at 3, 6 and 12 months of the study follow-up;
- Number of study participants reported last week's shortness of breath due to heart failure not requiring hospitalization (Patient-Reported Heart failure Severity) at 3, 6 and 12 months of the study follow-up;
- Number of study participants withdrawn from the study for any reason within a 12-month of the study follow-up;
- Costs of clinical service utilization for case management during the study follow-up;
- Costs incurred for incremental services, including costs for the major adverse cardiovascular and cerebrovascular event;

Along with studying the effectiveness of CYP2C19 genotype-guided treatment selection with clopidogrel and an alternative P2Y12 inhibitor, clinical case management processes in the real-life healthcare system and factors that positively and negatively impact the processes will be evaluated: healthcare processes, place of care, delivery of medical procedures, medication use, and management of comorbidities.

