Hypothesis	
The research question is how antiplatelet treatment for preventing major adverse cardiovascular events after ePCI works in chronic coronary artery disease when guided by personal genetic characteristics for drug metabolism.
 
The study aims to test two research hypotheses:
 
 
• CYP2C19 genotype-guided clopidogrel treatment ensures better clinical outcomes when compared with conventional treatment selection led without CYP2C19 genotyping.
 
• CYP2C19 genotype-guided antiplatelet treatment could be beneficially applied in real-world clinical practice.
 

Design	Multicenter, randomized, parallel-group controlled study

Primary Objectives	
The aim of the study is to evaluate CYP2C19 allele genotype-guided antiplatelet treatment outcomes.
 
The specific objectives of the study are:
 
 
— Pre-assignment and randomization of study participants into study arms for conventional and CYP2C19 genotype-guided antiplatelet treatment with clopidogrel or an alternative P2Y12 inhibitor;
 
— providing RT-PCR-based pre-, analytical and post-analytical processes of the study to ensure CYP2C19 *2, *3 allele profiling for detection of study participants with normal functioning (NFA) and loss of function (LOF) allele;
 
— Observation of clinical outcomes of patients in the study groups during the 12 months of treatment;
 
— Evaluation of processes and non-clinical outcomes of clinical case management;
 

Secondary Objectives	
 
— Implementation of the methods and procedures provided by the research protocol into a real clinical practice pipeline;
 
— Raising awareness and understanding of the role of laboratory services by bridging clinical, laboratory practice professionals and other stakeholders to achieve patient-centeredness and improve clinical outcomes;
 
— Evaluation of clinical practice models based on assessments of molecular markers;
 
— Disseminate study results through publishing a scientific paper in a peer-reviewed journal and abstracts for reporting study results.
 

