Other end-points of outcome measures	
 
— Composite of death from any cause, non-fatal myocardial infarction, stroke, or major bleeding within a 12-month of the study follow-up (Net adverse clinical events - NACEs);
 
— Composite of death from any cause, non-fatal myocardial infarction, or stroke within a 12-month of study follow-up (Major adverse cardio or cerebrovascular events - MACCEs);
 
— Composite of death from cardiovascular cause, non-fatal myocardial infarction, recurrent angina, or repeated revascularization (PCI or CABG) within a 12-month of study follow-up (Major adverse cardiovascular events - MACEs);
 
— Number of study participants whose health status was defined as good or satisfactory, or with the appearance of CVD symptoms, or with a significant inability to self-care (Patient-Reported Health Status) reported by the patient or patient caregiver at 3, 6 and 12 months of the study follow-up;
 
— Participants self-reported (or patient's caregiver reported) angina not required hospitalization (Patient-Reported Angina Not Required Hospitalization at 3, 6 and 12 months of the study follow-up;
 
— Participants reported (or patient's caregiver reported) last week's shortness of breath due to heart failure not requiring hospitalization (Patient-Reported Heart Failure Severity) at 3, 6 and 12 months of the study follow-up;
 
— Withdrawal for any reason within a 12-month of the study follow-up;
 
— Costs of clinical service utilization for case management during the study follow-up;
 
— Incremental costs incurred for real-world health care services, including costs for the MACCEs, MACEs and NACEs;
 

Other measures	
 
— Cardiometabolic risk factors and their control status;
 
— Total number of hospitalizations for any reason within 12 months of the study follow-up;
 
— Comorbidities;
 

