### 1.2. Anticipated Use of the Investigational Product

The investigational product can be used for CYP2C19 \*2, \*3 genotype-guided clopidogrel or an alternative P2Y12 inhibitor treatment of high-risk ASCVD patients for tailoring antiplatelet therapy to optimize the prevention of MACCE.

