## 2.4 Study Participant Selection

### 2.4.1 General Characteristics of Study Participants

Study participants are patients requiring treatment with clopidogrel or an alternative P2Y12 inhibitor following ePCI as a major cardiovascular clinical event for CAD.

Study participants will be selected based on a clinical model defined by stable CAD confirmed by ePCI. They have undergone coronary stenting within the past 12 weeks to reduce their risk, and despite this reduction, they are still at risk of developing recurrent MACCEs. To reduce the risk of subsequent MACCE, the patient with these clinical characteristics requires antiplatelet therapy with clopidogrel after coronary stenting. Carriers of CYP2C19 \*2, \*3 LOF alleles, as patients at complement risk due to expected resistance to clopidogrel treatment, will be given antiplatelet therapy with an alternative P2Y12 inhibitor to clopidogrel for prevention.

In contrast to primary PCI for the management of CAD STE/NSTE-ACS or coronary artery bypass grafting, patients selected with the study clinical model have a relatively lower risk of developing recurrent MACCEs. By equalizing or excluding complementary cardiovascular risky conditions, and co-morbidities, which will be achieved by using study participants' inclusion and exclusion criteria, precise antiplatelet therapy using P2Y12 inhibitors and ensuring adherence to treatment at baseline the probability of recurrent MACCE cases will be equal for the experimental and control arm of study participants. Thus, it will be possible to follow-up and evaluate the clinical outcomes of CYP2C19 genotype-guided as well as conventional treatment with P2Y12 inhibitors (clopidogrel or alternative) which is the aim of the study.

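### Both primary endpoints are deaths, although the research question and intended use concern preventing major adverse events; the MACCE composite already defined ranks below the secondary endpoints

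*Combined protocol and SAP*

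**What the plan says.** **The question and the product.** The Synopsis (Hypothesis) asks "how antiplatelet treatment for preventing major adverse cardiovascular events after ePCI works in chronic coronary artery disease". Section 1.2 gives the assay's use as "for tailoring antiplatelet therapy to optimize the prevention of MACCE". The first formal hypothesis in the Synopsis is broader and names no endpoint: "genotype-guided clopidogrel treatment ensures better clinical outcomes when compared with conventional treatment selection".

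**The primary endpoints.** Section 2.6.1 lists two: "Number of study participants who died from any cause (Death from Any Cause) within a 12-month of the study follow-up" and "Number of study participants who died from any cardiovascular cause (Death from Cardiovascular Cause) within a 12-month of the study follow-up". The Synopsis lists the same two.

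**Where the other events rank.** Non-fatal MI and stroke or TIA are secondary. The MACCE composite, "Number of study cases in each study arm with a composite of death from any cause, myocardial infarction, or stroke", comes in a third list, with NACE (the same events plus major bleeding). In the Synopsis that tier is headed "Other end-points of outcome measures" and also contains a MACE composite: cardiovascular death, non-fatal MI, recurrent angina or repeat revascularization. Section 2.6.1 calls the tier pre-specified endpoints and does not list MACE there. The headings differ but the rank is the same.

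**Risk level.** Section 2.4.1 says that, in contrast to primary PCI for acute coronary syndrome or bypass surgery, "patients selected with the study clinical model have a relatively lower risk of developing recurrent MACCEs". Section 3.2.1 puts the probability of MACCE at 1-10%, but for a list of 11 event types that includes recurrent angina, TIA, atrial fibrillation and heart failure. I found no death rate, and no rate for the three-part composite.

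**The concern.** The rationale in section 1.3 is that loss-of-function carriers treated with clopidogrel have more MACCEs. A primary analysis of deaths alone discards the non-fatal MIs and strokes through which much of any benefit would show. The plan does not say why death alone was made primary.

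Two things are at stake. A null primary result could be read as showing that guidance does not help, when most of the events to be prevented were not in the primary analysis. And in 240 patients followed for 12 months, deaths may be so few that the primary comparison says little even about mortality.

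**Working it through.** **1. The plan's own sample size.** Section 2.6.2, tool 2: control 0.6, experimental 0.4, ratio 2, two-sided alpha 0.05, power 0.8. With the pooled proportion p̄ = (0.6 + 2×0.4)/3 = 0.4667:

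n(control) = [1.960·√(1.5×0.4667×0.5333) + 0.8416·√(0.6×0.4 + 0.4×0.6/2)]² / 0.2² = (1.1976 + 0.5050)² / 0.04 = 72.5, rounded up to 73.

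The total is 73 + 146 = 219, against the stated 221, so the figure reproduces. At the planned 80 v 160 the power for 40% v 60% is 84%. These probabilities are attached to no named endpoint, and they lie far above even the 1-10% of section 3.2.1.

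**2. Deaths at 80 v 160.** Control mortality of 1%, 2% or 3% and a halving under guidance are my assumptions. Expected deaths = 80·p + 160·p/2. The chance of no control death is (1−p)^80. Power is exact, for the two-sided Fisher test at 0.05.

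| Assumed control mortality | Expected deaths, both groups | Chance of no control death | Fisher power |
|---|---|---|---|
| 1% | 1.6 | 45% | 2.4% |
| 2% | 3.2 | 20% | 7.4% |
| 3% | 4.8 | 9% | 11.4% |

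At 5% the expected number is 8.0 and power is 16%. With a risk ratio of 0.67 instead of 0.5, power at 1-3% is 2-7%. Cardiovascular deaths are a subset of all deaths, so the second primary endpoint cannot have more events.

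**3. Smallest result that reaches significance.** Suppose no guided participant dies and k controls die. The two-sided Fisher p is then C(80,k)/C(240,k).

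- k = 2: 3,160/28,680 = 0.110
- k = 3: 82,160/2,275,280 = 0.036

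So at least three control deaths are needed, and significance can turn on one death.

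**4. What MACCE as primary would give.** Any participant who dies from any cause has a MACCE, so the composite counts at least as many participants with an event as death does. How many more cannot be derived from the documents. As a borrowed range only, taking section 3.2.1's 1-10% as the control rate and halving it:

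| Control rate | Expected events, both groups | Fisher power |
|---|---|---|
| 1% | 1.6 | 2% |
| 5% | 8.0 | 16% |
| 10% | 16.0 | 27% |

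For 80% power at 10% v 5%, the formula in step 1 (p̄ = 0.0667) gives 312 controls, 936 in total.

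**5. Counting to 12 months.** Section 3.2.6 withdraws a participant once a MACCE or anticipated adverse medication effect is registered. Section 3.2.7 leaves further follow-up or withdrawal to an IRB recommendation. Section 3.3 treats further measures as no longer required. Section 2.6.1 counts deaths, MIs and strokes over 12 months. Read together, a death after a non-fatal event may go uncounted. So may an MI or stroke after, for example, angina, atrial fibrillation or minor bleeding, all of which are listed in section 3.2.1.

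**The case against.** A reader might infer that the primary result cannot answer the trial's question at all. The documents do not support that. Death is a component of MACCE, the formal hypothesis speaks only of better clinical outcomes, and Appendix 3 gives MACCE, MACE and NACE the same rate, hazard ratio, relative risk and benefit indicators as death. The composite will be analysed. The defect is one of ranking, and the primary endpoints are related to the question but too narrow for it.

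The low-risk argument has limits. The statement in section 2.4.1 concerns MACCE rather than death and is relative to higher-risk patients. It does not show that mortality is low in absolute terms, and it bears on the proposed endpoint as well.

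A reader might also take the 10% in section 3.2.1 as the expected rate of the composite, which would mean 24 events among 240 if guidance had no effect. That figure is the top of a range for a much wider list and cannot be carried over.

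All-cause death is the outcome least open to assessor judgement, and section 2.5.4 discloses treatment after randomization. That is a fair reason to prefer it, although the plan does not give it and it applies less to cardiovascular death, which needs a cause assigned. It stands as a cost of the change.

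Finally, the low power is mainly a sample-size problem that re-ranking does not cure. That also stands.

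**Conclusion.** The concern holds as a mismatch between question and primary endpoint, and it should be corrected. The question and intended use are about preventing major adverse events; the primary endpoints take in only the fatal part, and the composite that matches better is ranked third.

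On assumed control mortality of 1-3%, halved, about 2 to 5 deaths are expected and Fisher power is 2-11%. Both the mortality range and the halving are assumptions. It would be wrong to say that two deaths could make the primary result positive, since 2 v 0 gives p = 0.11.

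Making MACCE primary improves alignment and cannot lower the number of participants with a counted event, provided events are recorded to 12 months. It does not rescue the stated 80% power, which belongs to 40% v 60%.

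**What to change.** In the Synopsis endpoint rows and section 2.6.1:

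- Make the MACCE composite of section 2.6.1 (death from any cause, non-fatal MI or stroke within 12 months, counted as first event) the primary endpoint. State that the 11-event list of section 3.2.1 is not its definition.
- Make all-cause and cardiovascular death secondary components, and NACE the key net-benefit endpoint.
- Say why MACCE is preferred to the Synopsis MACE composite, because the research question's wording is the one the abbreviation list assigns to MACE.
- Do not carry the 0.4/0.6 power statement of section 2.6.2 over to the new primary endpoint. Justify a rate for the three-part composite and report the power that 240 patients give.
- Fix the event definitions. Section 2.5.2 already cites the universal definition of MI. The stroke references there are management guidelines, so a stroke definition must be written, and it must separate stroke from the TIA included in the secondary endpoint.
- Reconcile sections 3.2.6, 3.2.7 and 3.3 with the 12-month endpoints of section 2.6.1, so that later deaths, MIs and strokes are counted.

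**Cost.** An amendment to the endpoint hierarchy. The composite is already defined and endpoints are already assessed at 3, 6 and 12 months, so no new type of data is needed, but complete capture depends on the last item. MI and stroke are more open to judgement than death once treatment is known. Section 2.6.3 has data evaluated continuously, so the change must be made and dated before anyone reviews outcome data by arm.
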